## 10.0 Study Design / Methods

### Screening

[figure not shown]
Up to 40 participants will be screened for inclusion/exclusion criteria, and if enrolled, will attend up to 5 visits at the MUSC brain stimulation laboratory. Participants will sign consent before visit 1, including a urine pregnancy screen (if female). We expect this study to be completed over the span of 6-8 months.

Participants will be screened for taVNS and TMS contraindications before enrolling in the study and written informed consent will be obtained from all participants prior to participation in the experimental paradigm.

For more information on taVNS and TMS screening please see the uploaded taVNS screening form.

[figure not shown]
### Study Design

We will enroll 40 healthy individuals into a motor excitability prescreening visit (20Hz rTMS to motor cortex flanked by pre- and post-MEP), and from this prescreen cohort subsequently enroll a total of 24 healthy participants (of whom had increases in motor excitability in the prescreen) into a 4 visit, randomized, sham-controlled trial exploring various forms of neuromodulation on cortical excitability (Figure 1). We will first conduct a baseline measure of cortical excitability using a validated motor evoked potential (MEP) paradigm. Participants will then receive 20 minutes of one of four different stimulation conditions (active TMS, sham TMS, active taVNS, sham taVNS, paired taVNS/TMS, unpaired taVNS/TMS). MEPs will be then recorded immediately after stimulation, and every 10 minutes following for 30 minutes.

### Neurostimulation

All participants enrolled in the pilot dosing trial will receive TST by a trained therapist in the **QBAR CORE**. TST will be administered 3 times per week for 4 weeks (12 total sessions). Each session will last 1 hour, and participants will be connected to EMG electrode arrays that will sense movements while the affected limb is trained in functional tasks like reaching forward to hold a glass and drinking from it, picking up and using objects, fine motor task and dexterity training. During TST, taVNS will be delivered in a movement-gated fashion.

### Stimulation Parameters.

**rTMS:** 20 Hz rTMS will be delivered (using Magventure X100 system) to the motor hot spot of the left M1

region at 90% of rMT for 2.5 seconds ON and 10 seconds OFF. This will be repeated 40 times, for a total of 2,000 pulses of stimulation over 20-minutes. The stimulation target will be digitally marked using Brainsight neuronavigation for inter- and intra-session targeting validation.

**taVNS:** taVNS will be delivered (using a Digitimer constant current stimulation system) at the optimal stimulation parameters determined by our group (25Hz, 500us pulse width, 200% perceptual threshold) targeting the left anterior wall of the ear canal at a 50% duty cycle for 20 minutes.

**Paired taVNS/TMS:** We will synchronize taVNS with rTMS using MATLAB written software (Figure 2a). This software will deliver active/sham taVNS (25Hz, 500us PW, 200%PT) concurrently with active/sham 20Hz rTMS (2.5s ON, 10s OFF, 90% rMT) targeting the left M1 region (Figure 2b).

**Unpaired taVNS/TMS:** In this condition, active 20Hz rTMS (2.5s ON, 10s OFF, 90% rMT) will be delivered with active taVNS will be delivered in 2.5s trains during the rTMS using MATLAB written software. This software will deliver taVNS (25Hz, 500us PW, 200%PT) concurrently with 20Hz rTMS (2.5s ON, 10s OFF, 90% rMT) (Figure 2b).

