### Collected Measures :

#### MEPs using the Motor Cortex Excitability Recording Paradigm

Resting and active motor threshold will be found using PEST, and automated algorithm used to determine threshold. EMG recordings using Ag/AgCl electrodes will be placed on the subject's abductor pollicis brevis (APB) muscle in order to record motor evoked potentials (MEPs). The EMG recording electrodes will be connected to a standard Cambridge Electronics Device (CED) MEP system and MEPs will be recorded and analyzed with the associated Spike2 software. The level of stimulation required to produce a MEP of 1mV will be determined prior to collecting baseline MEPs. Up to 80 Baseline MEPs will be collected at the pre-determined stimulation output for 1mV. After the 20-minute randomized stimulation condition, up to 40 MEPs will be collected immediately after stimulation and at 10 minute intervals for 30 minutes.

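### The rTMS schedule does not add up: 40 cycles of 2.5 s ON and 10 s OFF take 8 min 20 s, not 20 minutes

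*Combined protocol and SAP*

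**What the plan says.** Section 10.0, Stimulation Parameters, opens the rTMS paragraph with the frequency and target: "20 Hz rTMS will be delivered (using Magventure X100 system) to the motor hot spot of the left M1". The train pattern follows: "region at 90% of rMT for 2.5 seconds ON and 10 seconds OFF". The next sentence gives repeats, pulse total and duration: "This will be repeated 40 times, for a total of 2,000 pulses of stimulation over 20-minutes".

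Both the train pattern and the 20 minutes are repeated elsewhere:

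- **Train pattern.** The paired condition delivers taVNS "concurrently with active/sham 20Hz rTMS (2.5s ON, 10s OFF, 90% rMT) targeting the left M1 region". The unpaired condition gives the same ON and OFF times twice, first in "In this condition, active 20Hz rTMS (2.5s ON, 10s OFF, 90% rMT) will be delivered".
- **Twenty minutes.** The Study Design subsection says "Participants will then receive 20 minutes of one of four different stimulation conditions". The Collected Measures subsection says "After the 20-minute randomized stimulation condition, up to 40 MEPs will be collected immediately after stimulation". The taVNS paragraph also sets 20 minutes for taVNS.

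No section mentions a pause, a second block or a longer interval between trains.

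**The concern.** Frequency, ON time, OFF time and number of trains fix the duration of an rTMS session. Here the duration they imply is less than half the one stated, so the document does not define a single schedule. Whoever programs the stimulator must drop at least one stated figure, and the choice changes the interval between trains, the end time of rTMS or the number of pulses.

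The timing of the readout is also at stake. The endpoints are MEPs at baseline and at 10-minute steps after stimulation (Section 4.0). The Motor-Evoked Potentials text in Section 3.0 counts those steps from the end of rTMS, whereas Collected Measures counts them from the end of the 20-minute condition. The two clocks coincide only if rTMS really lasts 20 minutes. Section 1.0 puts the duration of excitability gains at 10 to 60 minutes depending on the form of stimulation, so a delay of more than 10 minutes could use up the whole of a short-lived effect. Aim 2 asks whether timing matters, so this study in particular needs a defined train schedule.

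**Working it through.** **Inputs**, all from Stimulation Parameters in Section 10.0: frequency 20 Hz; ON 2.5 s; OFF 10 s; 40 repeats; stated total 2,000 pulses; stated duration 20 min = 1,200 s.

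**1. Pulse total.** Frequency × ON time × repeats = 20 × 2.5 × 40 = 2,000. The plan's figure is reproduced.

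**2. Duration.** Repeats × (ON + OFF) = 40 × (2.5 + 10) = 40 × 12.5 = 500 s = 8 min 20 s. The plan's 20 minutes is not reproduced. The shortfall is 1,200 − 500 = 700 s (11 min 40 s), and 500/1,200 = 42%.

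**3. Other readings of the same figures.**

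- No OFF period after the last train: 40 × 2.5 + 39 × 10 = 490 s = 8 min 10 s.
- 10 s taken as the whole cycle: 40 × 10 = 400 s = 6 min 40 s.

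Neither comes near 20 minutes.

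**4. What each repair would imply.**

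| Figures kept | Figure that changes | Trains | Pulses | rTMS duration |
|---|---|---|---|---|
| 40 trains, 2,000 pulses, 20 min | OFF = 1,200/40 − 2.5 = 27.5 s | 40 | 2,000 | 20 min |
| 40 trains, 2,000 pulses, 10 s OFF | Duration | 40 | 2,000 | 8 min 20 s |
| 10 s OFF, 20 min | Trains = 1,200/12.5 = 96; pulses = 96 × 50 = 4,800 | 96 | 4,800 | 20 min |

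Without a final OFF period, the first row needs (1,200 − 100)/39 = 28.2 s. The third row is 4,800/2,000 = 2.4 times the stated pulse total.

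**5. Effect on the MEP clock.** Suppose rTMS follows the second row and the session still runs to 20 minutes. The first post-stimulation MEP then falls 1,200 − 500 = 700 s (11 min 40 s) after the fortieth cycle ends. Counted from the last pulse it is 1,200 − 490 = 710 s (11 min 50 s). Either figure exceeds one 10-minute assessment step in a 30-minute follow-up. If rTMS is spread over the full 20 minutes, there is essentially no shift.

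**The case against.** The arithmetic is not in dispute. The case on the other side is that the consequences are narrower than they look.

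- **Dose.** Repeats and pulse total are both stated outright and agree with each other, so 4,800 pulses would require setting aside two explicit figures. This is a fair point. The likelier ambiguity is 10 s versus 27.5 s OFF, or 8 min 20 s versus 20 min, at a fixed 2,000 pulses.
- **MEP timing.** The shift of nearly 12 minutes is a worst case. It needs rTMS to end early while the session or taVNS continues. The paired and unpaired paragraphs describe the two stimulations as concurrent, which suggests that they end together, and Section 3.0 ties the MEPs to the end of rTMS. That also stands, but it leaves the conflict between Section 3.0 and Collected Measures, and taVNS has its own 20-minute instruction.
- **Bias between conditions.** The same pattern is given for active and sham rTMS, delivery is controlled by software, and the design is within-subject. A schedule programmed once would be common to all visits. Bias between conditions is therefore possible, chiefly in the Aim 1 comparison of taVNS alone with TMS alone, but it is not shown.
- **Prescreen.** The prescreening visit is described only as 20 Hz rTMS. Whether it uses this schedule is an inference.

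Figure 2b is not available and may show the intended timing. It could not make the written numbers agree.

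**Conclusion.** The rTMS schedule is wrong as written and has to be corrected. At the stated train pattern and repeats, rTMS lasts 500 s against a stated 1,200 s. This rests only on figures in the protocol and holds under every reading tried.

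The text does not show which figure is the slip. Frequency, ON time, repeats and pulse total are mutually consistent, so the conflict lies between the OFF interval and the duration, unless repeats and pulse total are both wrong together. The 2.4-fold pulse count applies only if 10 s OFF and 20 minutes are both followed. The shift of up to 11 min 40 s in the MEP clock (11 min 50 s from the last pulse) applies only if rTMS stops early within a 20-minute session. The defect matters even without those conditions, because the text leaves open how the intervention is delivered and when the endpoint clock starts.

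**What to change.** 1. Make the OFF interval, number of trains, pulse total and duration agree in Stimulation Parameters. At 40 trains and 2,000 pulses, the consistent choices are 27.5 s OFF over 20 minutes or 10 s OFF over 8 min 20 s. Which was intended is for the investigators to say.
2. Carry the chosen values into the paired and unpaired paragraphs, for active and sham rTMS alike, and into the 20-minute statements in Study Design and Collected Measures. State whether the prescreening visit uses the same schedule.
3. Say whether taVNS and rTMS end together, and define MEP time zero by the same event in every condition, so that Section 3.0 and Collected Measures give one clock.
4. Check the MATLAB and stimulator programs against the corrected text. If sessions have already been run, report the schedule actually delivered.

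The cost is protocol wording and a program check. No extra participants or visits are needed.

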### Sham Controls:

rTMS sham - We will use the magventure rTMS sham procedure in which a sham coil is placed on top of scalp stimulating electrodes which will be placed on the scalp on or near the motor cortex. This setup mimics the sensation of rTMS, and participants cannot tell which condition they are receiving beyond chance.

taVNS sham – We will use a sham similar to that reported in our prior work, with electrodes placed on the earlobe – an ear target with limited to no ABVN innervation.

### Collected Measures :

#### MEPs using the Motor Cortex Excitability Recording Paradigm

Resting and active motor threshold will be found using PEST, and automated algorithm used to determine threshold. EMG recordings using Ag/AgCl electrodes will be placed on the subject's abductor pollicis brevis (APB) muscle in order to record motor evoked potentials (MEPs). The EMG recording electrodes will be connected to a standard Cambridge Electronics Device (CED) MEP system and MEPs will be recorded and analyzed with the associated Spike2 software. The level of stimulation required to produce a MEP of 1mV will be determined prior to collecting baseline MEPs. Up to 80 Baseline MEPs will be collected at the pre-determined stimulation output for 1mV. After the 20-minute randomized stimulation condition, up to 40 MEPs will be collected immediately after stimulation and at 10 minute intervals for 30 minutes.

### Estimated Difficulties, Limitations and Time Frames

*Estimated Difficulties.* Healthy control MEP studies have been conducted in our laboratory for over 20 years – with minimal difficulty. For this particular study the estimated difficulty will likely be minimizing dropout over 5 experimental visits.

*Limitations.* There are two potential limitations with these studies. The first is tolerability of electrical nerve stimulation of the tragus and earlobe. Although we do not anticipate any issues, drop-out may be an issue due to discomfort of the stimulation.

*Estimated Time Frames.* We plan on completing this study over the next 6-8 months.

### 11.0 Data Management

Limited demographic and personal health history data will be collected during the phone screen in order to screen out participants with conditions that might confound the research or put them at risk for an

adverse event. All screening data will be kept in a binder in the locked office in the Brain Stimulation Lab as per the requirements of the IRB. Screening data collected from participants who do not qualify for the study will be securely destroyed.

**Power Calculation:** Our proposal utilizes a within-subject design, in which each subject will be their own control. Using the low end of a range of effect sizes (derived from 0.06 partial eta) from prior excitatory TMS/MEP studies (11-13) the proposed study will be sufficiently powered to detect a change in MEP magnitude due to an experimental intervention (paired active/sham rTMS, active/sham taVNS, unpaired taVNS/TMS) using a one-way ANOVA at 80% power and 5% significance level.

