Can we enhance the effects of rTMS on motor cortex? A different brain stimulation modality, cervically implanted vagus nerve stimulation (cVNS) can enhance neuroplasticity and facilitate rehabilitation, especially when paired with an intervention such as task-specific training(19, 20). There is a new noninvasive form of this method, transcutaneous auricular vagus nerve stimulation (taVNS). This may also facilitate plasticity and is being investigated in the enhancement of motor learning and recovery in a specific paired fashion. The timing of the paired VNS is critical to the desired neuroplastic changes(21-23), as the behavioral effects of paired therapy disappear when behavior is not intricately synchronized with stimulation. Could pairing taVNS with TMS boost the effects of TMS on cortex, and potentially emerge as a stroke recovery tool? As a first step in this direction, we propose a basic, mechanistic pilot study exploring the use of paired taVNS/TMS to further enhance motor cortex excitability in 24 healthy individuals in a 4 visit, randomized, sham controlled, counterbalanced study.

**Aim 1. Determine the effects of taVNS on motor cortex excitability.** We hypothesize that taVNS alone (sham rTMS + active taVNS) will induce increases in motor cortex excitability (post-stimulation compared to baseline). We believe these changes will be of a lesser magnitude than those of TMS alone (active rTMS + sham taVNS) due to the indirect mechanistic approach of taVNS.

**Aim 2. Determine whether taVNS-paired TMS is more effective at inducing cortical excitability than TMS alone.** We hypothesize that pairing two forms of neuromodulation (active rTMS + active taVNS) will increase TMS-induced cortical excitability in the motor cortex when compared to single modality approaches (active rTMS + sham taVNS; sham rTMS + active taVNS). Furthermore, we believe this increase is timing sensitive, and the paired approach will induce larger TMS-induced cortical excitability compared to unpaired neuromodulation (active taVNS + active taVNS).

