#### **rTMS-induced increases in cortical excitability improve functional outcomes post-stroke**

Repetitive transcranial magnetic stimulation (rTMS) is a safe, noninvasive form of cortical brain stimulation that transiently induces neurophysiologic changes. When delivered at sub-threshold intensity to the motor cortex has been used to correct post-stroke interhemispheric-imbalance by either reducing excitability in the contralateral motor cortex or increasing excitability in the ipsilateral motor cortex. (17, 18).

Studies have demonstrated that single sessions of high frequency stimulation (20Hz) of the motor cortex elicits transient increases in MEP size. This modulation of cortical excitability makes rTMS an exciting tool for motor rehabilitation, as motor cortex excitability is involved in the learning of motor skills (26, 27). rTMS is a safe method of inducing motor cortex excitability and is in neurorehabilitation to either inhibit contralateral motor cortex or excite ipsilateral motor cortex in order to restore interhemispheric competition post-stroke.

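### The stated 80% power does not follow from a partial eta of 0.06 as written; read as partial eta squared, 24 participants give between 37% and 83%, depending on a scale and a correlation that the plan does not state.

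*Combined protocol and SAP*

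**What the plan says.** The only power statement in the document is a short paragraph in section 11.0 (Data Management). It sets out the design, "Our proposal utilizes a within-subject design, in which each subject will be their own control"; the effect size, "Using the low end of a range of effect sizes (derived from 0.06 partial eta) from prior excitatory TMS/MEP studies (11-13"); and the test, "using a one-way ANOVA at 80% power and 5% significance level". On that basis it calls the study sufficiently powered.

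The paragraph gives no sample size, number of conditions, Cohen's f, within-person correlation or sphericity assumption. The sample size comes from elsewhere. Section 1.0 describes a study "in 24 healthy individuals in a 4 visit, randomized, sham controlled, counterbalanced study", and Study Design in section 10.0 says the investigators will "subsequently enroll a total of 24 healthy participants" from the prescreened cohort. The number of conditions is also in Study Design: "Participants will then receive 20 minutes of one of four different stimulation conditions".

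**The concern.** The 80% cannot be reproduced from the paragraph alone, for two reasons.

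- **The quantity is unclear.** Eta and eta squared differ greatly at this size. A partial eta of 0.06 is a partial eta squared of 0.0036.
- **The scale is unclear.** A partial eta squared from a repeated-measures analysis has already had between-person variance removed. One from a between-person analysis has not. The same 0.06 therefore implies different power depending on its source. If a within-subject value is converted to f and then credited with a within-person correlation, the benefit of the within-subject design is counted twice.

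The 80% is the only operating characteristic the protocol offers. If the 0.06 is a within-subject value, a true effect of that size would be missed about 63% of the time (100% minus 37%) by the four-level test, although the plan calls the study sufficiently powered.

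**Working it through.** **Inputs from the document.** N = 24 (sections 1.0 and 10.0); m = 4 conditions (Study Design); two-sided 5% level, one-way ANOVA, within-subject design, effect 0.06 (section 11.0).

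**Assumptions, because the document is silent.** All 24 complete; sphericity (epsilon = 1) unless stated; correlation rho varied. The test is the within-subject F with df1 = m − 1 = 3 and df2 = (N − 1)(m − 1) = 69. Power is the probability that a noncentral F with noncentrality lambda exceeds the 5% critical value of 2.74.

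**1. Reproducing the plan's figure.** Read 0.06 as partial eta squared on the between-person scale:

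- f² = 0.06/0.94 = 0.0638, so f = 0.253.
- lambda = f² × N × m/(1 − rho) = 0.0638 × 96/(1 − rho).

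| rho | lambda | power |
|---|---|---|
| 0 | 6.13 | 50% |
| 0.3 | 8.75 | 67% |
| 0.4 | 10.21 | 74% |
| 0.5 | 12.26 | 83% |
| 0.7 | 20.43 | 97% |

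Power reaches 80% at rho = 0.47. With f rounded to 0.25 and rho = 0.5, power is 79.7% at N = 23 and 81.7% at N = 24, so the smallest adequate sample is exactly the planned 24.

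This reading has little slack at rho = 0.5 (f = 0.253). Power falls to 74% if epsilon is 0.75. It is 81% with 23 completers, 79% with 22 and 74% with 20. Section 10.0 names dropout over five visits as the expected difficulty but makes no allowance for it.

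**2. Partial eta squared already on the within-subject scale.**

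- lambda = f² × (N − 1)(m − 1) = 0.0638 × 69 = 4.40; power 37%.
- Smallest N for 80%: 60 (lambda = 0.0638 × 59 × 3 = 11.30; power 80.6%).

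**3. Literal partial eta of 0.06.**

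- Partial eta squared = 0.06² = 0.0036; f² = 0.0036/0.9964 = 0.00361; f = 0.060.
- Within-subject scale: lambda = 0.00361 × 69 = 0.25; power 6.4%.
- Between-person scale: 7.0% at rho = 0, 9.2% at rho = 0.5, and 16% even at rho = 0.8.
- Smallest N for 80%: 379 (between-person scale, rho = 0.5) to 1,009 (within-subject scale).

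**4. What 24 completers can detect, whatever the source scale.**

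- 80% power on 3 and 69 df needs lambda = 11.54, so within-subject partial eta squared = 11.54/(11.54 + 69) = 0.143, about 2.4 times 0.06.
- Single paired contrast, two-sided t on 23 df: a mean difference of 0.6 SD of the differences has noncentrality 0.6 × √24 = 2.94 and power 80%.

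**5. Sensitivity to the number of levels.** Study Design says four conditions but lists six labels in brackets. With 5 or 6 levels, power is 88% or 92% for reading 1 at rho = 0.5, 44% or 50% for reading 2, and at most about 19% for reading 3. The contrast between the readings remains.

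**The case against.** The strongest reply is that the sponsor's figure does reproduce. With f = 0.25 and a correlation of 0.5, the smallest N for 80% is exactly 24. That makes a dropped word, squared, by far the likeliest explanation of the wording, since the literal reading would need hundreds of participants. This stands: the 6-9% shows that the sentence is wrong as written, not that the study has 6-9% power.

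A reader might also infer that the sponsor counted the within-subject benefit twice and that true power is 37%. The documents do not support that. Section 11.0 says only that the effect size was derived from a range in three cited studies, without saying how. Section 2.0 says that "single sessions of high frequency stimulation (20Hz) of the motor cortex elicits transient increases in MEP size", which suggests before/after measurement in the same people. But that sentence reports no effect size and no error term, and is not tied to those three studies. Double counting is possible but not shown.

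Nor does the shortfall hold for every ANOVA one might run. Each condition has a baseline and four later recordings (0, 10, 20 and 30 minutes). A condition-by-time test would have 3 × 4 = 12 and 23 × 12 = 276 df. At a within-subject partial eta squared of 0.06, lambda is 0.0638 × 276 = 17.62 and power is 79%, assuming sphericity. The plan names a one-way ANOVA, so the figures above apply to the test it states, but only to that test.

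Finally, section 1.0 calls this a basic, mechanistic pilot. A pilot need not promise 80% power. This one does, so the claim should be traceable to its inputs.

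**Conclusion.** The point holds as a should-fix. The stated 80% does not follow from the input as written. After the probable correction to partial eta squared, it follows only with a between-person scale, a within-person correlation of about 0.47 or more, sphericity and almost no dropout, none of which the plan states. If the source value is on the within-subject scale, power for the four-level one-way test is 37%.

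The scale is unknown, so 37% is conditional and the study is not shown to be underpowered. The range to report for 0.06 is 37% (within-subject scale) to 83% (between-person scale, correlation 0.5), assuming 24 completers, four conditions and sphericity. A correlation above 0.5 would raise the upper figure but leave the 37% unchanged.

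**What to change.** In section 11.0, change partial eta to partial eta squared and restate the power as what the design delivers. Suggested text:

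*With 24 completers, a within-subject comparison of four conditions (3 and 69 df, 5% level, sphericity assumed) has 80% power for a within-subject partial eta squared of 0.14; a single paired contrast has 80% power for a mean difference of 0.6 SD of the differences.*

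Keep the 80% claim for 0.06 only if the paragraph also states that the source value is on the between-person scale and gives the assumed correlation (about 0.5). Otherwise report the range 37-83% for 0.06.

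The cost is one rewritten paragraph and no extra participants. The downside is that the stated power becomes less favourable.

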#### **Motor-Evoked Potentials.**

**MEP Recordings.** EMG recordings using Ag/Ag Chloride electrodes will be placed on the subject's hand muscle in order to record motor excitability. The EMG recording electrodes will be connected to a standard CED (Cambridge Electronics Device) amplifier and pre-amplifier. Spike2 software will be used to analyze and record the MEPs. The level of stimulation required to produce a MEP of 1mV will be determined prior to collecting baseline MEPs. Baseline MEPs will be collected at the pre-determined stimulation output for 1mV. Another series of pulses will be analyzed in comparison with the first. If the average amplitude is within 25%, we will proceed with experiment. If not, another series of baseline pulses will be obtained repeating the above process, up to 4 times. If the baseline remains highly variable, the participant will be withdrawn. Following rTMS stimulation, the same pattern of single pulses will be recorded at 0, 10, 20, 30..

The key assumption that underlies the use of MEP measurements as a "read-out" of upstream processes influencing the motor system is that the amplitude of MEPs recorded (via EMG) from peripheral muscles is a product of top-down influences on M1 (such as attention/volitional control), combined with changes in excitatory/inhibitory pre-synaptic (inter)neuronal balance (i.e. due to rTMS at the stimulation site), and the post-synaptic excitability of corticospinal output projections (Bestmann and Krakauer, 2015). This method has been well-established as safe and reliable in the field of TMS research and in the brain stimulation laboratory.

[figure not shown]
**Neuronavigation.** Brainsight Neuronavigation equipment and software will be used (<https://www.rogue-research.com/tms/brainsight-tms/>) to help ensure that the stimulation site remains unchanged during and between recordings and thereby decrease MEP variability.

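### The only named analysis, a one-way ANOVA, gives no MEP scale and no role for the baseline taken before stimulation; a baseline-adjusted within-subject model is the better default, with a gain from nil to substantial

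*Combined protocol and SAP*

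**What the plan says.** There is no separate analysis section. The one analysis named is in the power paragraph of section 11.0, where the study is said to be powered "to detect a change in MEP magnitude due to an experimental intervention", "using a one-way ANOVA at 80% power and 5% significance level". The effect size is "derived from 0.06 partial eta". The same paragraph describes the comparison as within-subject: "Our proposal utilizes a within-subject design, in which each subject will be their own control".

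Section 10.0 (Study Design) plans to "subsequently enroll a total of 24 healthy participants" over four visits. Section 1.0 calls the design randomized and counterbalanced.

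The baseline is described in two places. Section 10.0 (Collected Measures) says: "Up to 80 Baseline MEPs will be collected at the pre-determined stimulation output for 1mV". Section 3.0 (Motor-Evoked Potentials) adds a stability check: "Another series of pulses will be analyzed in comparison with the first". The experiment proceeds if the averages agree within 25%; otherwise the baseline is repeated, up to four times. Post-stimulation MEPs follow at 0, 10, 20 and 30 minutes. Aim 1 compares post-stimulation values with baseline but does not say how.

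Nowhere do the documents give a scale or transformation, a baseline covariate, a visit-order term, or a rule for combining the four post-stimulation blocks.

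**The concern.** Baseline has to enter the analysis somehow, since Aim 1 is framed against it, but the plan leaves the route open. Difference, percentage, ratio, post-only and covariate-adjusted analyses all fit the wording, and they can give different answers in 24 people. Leaving the choice until the data are in hand invites selection among them.

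The options also differ in precision. Every session is tuned to the same 1 mV target, so part of the remaining visit-to-visit spread in baseline is likely to be measurement noise. A change score fixes the baseline slope at 1 and carries that noise into the outcome. A post-only analysis fixes the slope at 0 and discards whatever the baseline predicts. Covariate adjustment estimates the slope.

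Amplitudes are positive, calibrated to a common target, and checked for stability in percentage terms. This makes a log scale, with effects reported as ratios, a natural choice.

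**Working it through.** **1. The plan's own figure.** Inputs from the documents: partial eta 0.06 (read as partial eta squared), 24 participants, four conditions, 80% power, 5% level. Assumed, because no value is given: correlation rho between repeated measures, and sphericity.

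- f² = 0.06/0.94 = 0.0638, so f = 0.253.
- One-way repeated-measures ANOVA, m = 4, rho = 0.5: lambda = f² × n × m/(1 − rho) = 0.0638 × 24 × 4/0.5 = 12.26, on 3 and 69 degrees of freedom.
- Power is 0.826 at n = 24, and 23 participants are enough for 80%. With f rounded to 0.25, N is exactly 24 and power is 0.817.

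So 24 is reproduced, but only at an assumed rho of 0.5. At rho = 0, 0.3 and 0.7, power at n = 24 is 0.50, 0.67 and 0.97.

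**2. Precision of three ways to use baseline, on one common scale.** Set the post-stimulation variance to 1. Let k = SD baseline/SD post and let r be the baseline-post correlation, both taken within participant across visits.

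- Change score: 1 + k² − 2rk
- Post-only: 1
- Baseline as covariate: 1 − r²

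The change score's excess over adjustment is (1 + k² − 2rk) − (1 − r²) = (k − r)². The post-only excess is r². Neither can be negative. A change score is worse than ignoring baseline when k² − 2rk > 0, that is, when r < k/2.

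| k | r | Covariate | Change | Ratio to change | Ratio to post-only |
|---|---|---|---|---|---|
| 1 | 0.3 | 0.91 | 1.40 | 0.65 | 0.91 |
| 1 | 0.5 | 0.75 | 1.00 | 0.75 | 0.75 |
| 1 | 0.7 | 0.51 | 0.60 | 0.85 | 0.51 |
| 0.5 | 0.3 | 0.91 | 0.95 | 0.96 | 0.91 |
| 0.5 | 0.5 | 0.75 | 0.75 | 1.00 | 0.75 |
| 0.5 | 0.7 | 0.51 | 0.55 | 0.93 | 0.51 |

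**3. What this means for power.** Suppose the 0.826 of step 1 belongs to a change score. Divide lambda by the variance ratio and deduct one degree of freedom. Power at n = 24 becomes 0.957, 0.925 and 0.887 at k = 1 (r = 0.3, 0.5, 0.7), and 0.843, 0.825 and 0.855 at k = 0.5. These figures inherit the assumed rho of 0.5.

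**4. Simulation.** Settings: 1,000 runs each, 24 participants, four conditions, lognormal MEPs, one condition shifted by 0.8 post SDs on the log scale. The Monte Carlo standard error is about √(0.8 × 0.2/1000) = 0.013.

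| Log SD baseline, post | r | Raw change | Log change | Log, baseline-adjusted |
|---|---|---|---|---|
| 0.1, 0.3 | 0.3 | 0.80 | 0.82 | 0.81 |
| 0.2, 0.4 | 0.3 | 0.77 | 0.79 | 0.82 |
| 0.2, 0.4 | 0.7 | 0.92 | 0.97 | 0.98 |
| 0.4, 0.4 | 0.3 | 0.65 | 0.63 | 0.85 |

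The first row has k = 0.1/0.3 = 0.33, close to r, so adjustment and log change are level within simulation error, as step 2 predicts. Where baseline carried no information (r = 0), log adjusted power was 0.79 to 0.80 against 0.80 to 0.81 for log post-only. That is the cost of the extra parameter.

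**The case against.** The strongest reply is that the plan never commits to an inefficient analysis. A reader might infer from section 11.0 that raw-scale change scores are planned. The documents do not say so: no scale appears anywhere, and a change due to an intervention may simply mean an effect. The 25% stability rule, if anything, shows the team thinking in percentages. This stands, so the point is about what is left unspecified and which method is the better default.

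A reader might also infer a guaranteed, quantified gain. That does not stand either. The larger figures need k = 1, whereas 1 mV calibration, the stability check and up to 80 baseline pulses against up to 40 per post block all suggest a smaller baseline SD. At k = 0.5 the advantage over a change score nearly disappears. Likewise, r below 0.5 as the point where change scores lose to ignoring baseline holds only at k = 1; in general it is r below k/2.

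Nor can one conclude that the study has no power to spare. Step 1 shows power from 0.50 to 0.97 depending on a correlation that the plan does not state.

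Finally, the log advantage assumes right-skewed, multiplicative data, and the documents give no MEP distribution. That is a fair caution. The case for adjustment holds on either scale.

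**Conclusion.** The concern holds in this form: the only named analysis leaves the MEP outcome and its scale undefined and gives the collected baseline no stated role as a covariate. A baseline-adjusted within-subject model is the better default because, on the same scale and in large samples, it cannot be less precise than a change score or a post-only analysis, for about one degree of freedom.

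The size of the gain is not known. Against a change score, the variance falls by 15% to 35% for r from 0.7 down to 0.3 if k = 1, by 0% to about 7% over the same range if k = 0.5, and not at all when r = k. Against a post-only analysis, it falls by r². Both r and k are assumptions here. Reading the plan's analysis as a repeated-measures ANOVA rests on its within-subject wording. This should be changed, but it does not show that the planned analysis would be invalid or underpowered.

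**What to change.** Replace the one-way ANOVA with a pre-specified within-subject mixed model:

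- **Outcome:** log mean post-stimulation MEP amplitude in each block.
- **Covariate:** that visit's log baseline, stating which accepted baseline series are averaged. Enter it so that the slope is the within-participant one, for example as the visit's deviation from the participant's own mean, with that mean also in the model.
- **Fixed effects:** condition, time block and visit order.
- **Random effects:** participant and participant-by-visit, because blocks within a visit are correlated. Alternatively, average the four post-stimulation blocks and drop the participant-by-visit and time terms.
- **Reporting:** condition effects as ratios with confidence intervals.

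State the within-subject correlation behind the sample size of 24 and, if prior laboratory data allow, give r and k as well.

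The cost is analysis-plan wording, modest extra analysis work and about one degree of freedom for the covariate. No additional data, visits or participants are needed.
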